Overview: We will conduct an open-label, randomized controlled trial to assess the effectiveness and safety of treating iron-deficiency anemia in pregnant women with intravenous iron compared with oral iron. We test the *hypothesis* that treating iron-deficiency anemia with intravenous iron is associated with improved maternal and neonatal outcomes compared with oral iron. We will use broad inclusion criteria and analyze data using the intention-to-treat principle to increase generalizability of the findings.

Inclusion & exclusion criteria:

Inclusion criteria:

- Pregnant women
- 18 years or older
- Diagnosed with iron-deficiency anemia
 - Serum ferritin <30ug
 - o Hgb <10 g/dl
- Between 24 34 weeks gestation
- Plan to deliver at an in-network hospital
- Able and willing to give informed consent

Exclusion criteria:

- Diagnosis of non-iron-deficiency anemia
- Multiple gestation
- Known or suspected major fetal anomaly or aneuploidy
- Planned delivery at out-of-network hospital
- Unable or unwilling to give consent

Study outcomes:

Primary outcome: The primary outcome of the trial is maternal anemia, defined as Hgb <11mg/dl, on admission for labor and delivery.

Secondary outcomes:

- 1. Safety:
 - i. Mild/moderate infusion reactions: chest tightness, itching, urticaria, flushing, nausea/vomiting, arthralgia, back or joint aches, mild shortness of breath, tachycardia, hypertension or hypotension, abdominal pain, diarrhea, peripheral edema, headache, dizziness, syncope, or numbness.
 - ii. Major infusion reaction: anaphylaxis-like reaction, seizures, or non-reassuring fetal heart rate tracing.

2. Maternal outcomes:

- i. Hgb at admission to labor and delivery
- ii. Hgb on postpartum day 1
- iii. Ferritin at admission to labor and delivery
- iv. blood transfusion
- v. mode of delivery
- vi. postpartum disposition
- vii. readmission

3. Neonatal outcomes

- i. gestational age at delivery
- ii. birth weight
- iii. cord gases (if performed as SOC)
- iv. umbilical artery lactate (if performed as SOC)
- v. APGAR scores
- vi. Hgb (obtained from cord blood)
- vii. Ferritin (obtained from cord blood)
- viii. neonatal morbidities
- ix. postpartum disposition

Screening:

[figure not shown]

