Maternal blood draw: Serum ferritin	SOC			х	
Cord blood collection & processing (Hgb & ferritin; cord gas and/or lactate if performed as clinical necessity)				Х	
Delivery & neonatal outcomes via chart abstraction					Х

^{*}If ferumoxytol is administered due to shortage of iron dextran, two infusions will occur in the prenatal period as outlined in the randomization section of this document. The post-infusion phone call will occur 48-72 hours after the second infusion.

Data analysis: Analyses will follow the intention to treat principle, in which patients will be analyzed in the group to which they were randomized whether or not they received the assigned treatment. Continuous variables will be compared using the Student's t-test or Mann Whitney t test, as appropriate. Categorical variables will be compared using the t or Fisher's exact test, as appropriate. We will calculate crude and unadjusted risk estimates and differences. We will use multivariable logistic regression to adjust for potential confounders. We will estimate the number needed to treat to prevent occurrence of one primary outcome.

Sample size estimation: Based on institutional data the baseline rate of anemia (Hgb<11mg/dl) on admission to labor and delivery among women on supplemental oral iron is 38.5%. We estimate that 108 patients will provide 80% power to detect a 60% or greater relative difference in anemia (38.5% versus ≤15.4%) with intravenous iron (alpha=0.05, 2-tailed test). We will recruit **120 patients** to account for an anticipated 10% loss to follow-up (**Table 1**).

The anticipated effect size of 60% is plausible and conservative. A study by Al *et al.*, the only study that reported the outcome of Hgb <11 at the time of delivery, showed an effect size of 88% (4.4% versus 37.8%, RR 0.12, 95% CI 0.03, 0.48).⁴ Based on preliminary data showing that 10 pregnant women received intravenous iron in 6 weeks at the Washington University Medical Center, we anticipate that the 124 patients will be recruited within 15 months.

Table 1: Sample size estimation (Baseline: 38.5%, Power: 80%, alpha 0.05, loss: 10%)				
Risk Estimate RR (%)	Anticipated Rate	N	N+10%	
0.67 (33)	25.8%	418	460	
0.60 (40)	23.1%	276	304	
0.50 (50)	19.3%	168	185	
0.40 (60)	15.4%	108	120	
0.33 (67)	12.7%	82	90	
0.30 (70)	11.6%	74	81	

HUMAN SUBJECTS PROTECTION

Assessment of Risks

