- v. The study team will monitor, document and report to the Institutional Review Board, any adverse events among study participants per the plan detailed below.

Reportable Events

The PI at each site will oversee the safety of the study at his/her site. During the study, the investigator or study site personnel will be responsible for querying and recording adverse events (AEs) and serious adverse events (SAEs), as detailed below.

Types of Reportable Events:

Serious Adverse Events (SAE)

The site must report all SAEs to the lead site, whether or not they result from study participation, within 24 hours of learning of the event. A serious adverse event (SAE) is any adverse event occurring within the timelines specified in the protocol that results in any of the following outcomes:

- Death
- Life-threatening situation (subject is at immediate risk of death)
- Inpatient hospitalization or prolongation of existing hospitalization
- Persistent or significant disability/incapacity
- Congenital anomaly/birth defect in the offspring of a subject who received study drug
- Important medical events that may not result in death, be immediately life-threatening, or require hospitalization, may be considered an SAE when, based upon appropriate medical judgment, they may jeopardize the subject and may require medical or surgical intervention to prevent one of the outcomes listed in this definition.

Adverse Events (AE)

An adverse event is any untoward medical occurrence in a clinical investigation subject administered an investigational product and which does not necessarily have to have a causal relationship with this treatment. An AE can, therefore, be any unfavorable and unintended sign (that could include a clinically significant abnormal laboratory finding), symptom, or disease temporally associated with the use of a medicinal product, whether or not considered related to the medicinal product.

For this study, abnormal laboratory findings (e.g., clinical chemistry, hematology) or other abnormal assessments (e.g., electrocardiogram, X-rays, vital signs) per se are not reported as AEs. Only the Adverse Events of Special Interest (AESI) defined below will be recorded on the CRFs and in the subject's chart.

Adverse Events of Special Interest (AESI)

Adverse events of particular clinical importance (other than SAEs mentioned above) will be classified as adverse events of special interest (AESIs). For this study, AESIs refer to:

• Mild/moderate reactions:

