- venipuncture complications (blood clot or infection)
- o bowel changes (constipation or diarrhea)
- chest tightness
- itching
- o urticaria
- flushing
- o nausea/vomiting
- o abdominal pain
- o peripheral edema
- arthralgia
- o new onset back or joint aches
- o mild shortness of breath
- tachycardia
- o severe hypertension (For infusion group: confined to infusion timeframe only)
- o severe hypotension (For infusion group: confined to infusion timeframe only)
- o neurological changes (syncope, dizziness, headache) (For infusion group: confined to infusion timeframe only)

Major reactions:

- o anaphylaxis-like reaction (For infusion group: confined to infusion timeframe only)
- o seizures (For infusion group: confined to infusion timeframe only)
- o non-reassuring fetal heart rate tracing (For infusion group: confined to infusion timeframe only)

Assessing and Documenting Reportable Events:

Subjects will be evaluated for adverse events in the following manner:

- Routine monitoring by infusion nurses during the IV iron treatment, with data obtained from the subject's EMR by research staff.
- Subjects will be called by research staff 48-72 hours after infusion to assess for transfusion reactions.
- Subjects on oral iron therapy will be monitored via their EMR and via contact with research staff as outlined in schedule of events

An adverse event report will be generated for each event that will include the following:

- Date of event discovery
- Severity (mild, moderate, severe, life threatening/disabling, death)
- Relationship to treatment
- Action taken
- Outcome
- Expected or not
- Date reported
- Relevant notes/chart records/supporting documentation to corroborate the event
- To whom event was reported (i.e. IRB, lead site, etc.)
 - Non- serious AESIs will be reported to the lead site within 5 days of discovery, and to the IRB at renewal.
 - SAEs and SAESIs will be reported within 24 hours of discovery to the IRB and the lead site.

Relationship of Reportable Events:

An investigator must make the determination of relationship to the drug for each SAE and/or AESI. The relationship to the drug should be assessed using the guidelines presented in the table below.

Relationship to Drug	Description
Related	Previously known toxicity of agent; or
	 Follows a reasonable temporal sequence from administration of the drug; or
	• Follows a known or expected response pattern to the suspected intervention; or

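### Six of 19 AESI lines are confined to an undefined infusion timeframe in the IV arm only, and the AESI list does not fully match the infusion-reaction outcome

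*Combined protocol and SAP*

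**What the plan says.** **Objective and outcome.** The Overview under Study Design and Methods says that the trial will "assess the effectiveness and safety of treating iron-deficiency anemia in pregnant women with intravenous iron compared with oral iron". Safety is the first secondary outcome, and its two lists are labelled infusion reactions. The mild/moderate list includes "arthralgia, back or joint aches, mild shortness of breath" and then "tachycardia, hypertension or hypotension, abdominal pain, diarrhea, peripheral edema, headache, dizziness, syncope, or numbness". The major list has three items. Neither list has a time limit.

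**Recording.** The Adverse Events paragraph under Reportable Events says: "Only the Adverse Events of Special Interest (AESI) defined below will be recorded on the CRFs". It also excludes abnormal vital signs as such from AE reporting. SAEs have their own route and are reported in both arms.

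**The AESI list.** Six lines carry a limit for the infusion group, such as "severe hypertension (For infusion group: confined to infusion timeframe only" and "non-reassuring fetal heart rate tracing (For infusion group: confined to infusion timeframe only". The aches line reads "new onset back or joint aches".

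**Contacts.** The IV arm has nurse monitoring at the infusion and a phone call 48-72 hours later. The oral arm has EMR review, a contact 2-4 weeks after randomization, and a self-report at delivery, or by phone up to 2 days after discharge.

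**Analysis.** The Data analysis paragraph has one general rule and makes no exception for safety: "Categorical variables will be compared using the t or Fisher's exact test, as appropriate".

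**The concern.** Two separate things go wrong.

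First, the same non-serious event can be an AESI in one arm and not in the other. In the IV arm, an event on one of the six lines outside the timeframe is not an AESI and so need not reach the CRF. In the oral arm the same event has no stated time limit. Someone who later compares the arms on these lines, which the objective invites, would be comparing counts made under different rules. The difference could not be fully undone afterwards. The listed contents of an event report include the date of discovery but not the date of onset, and an event that was never logged has no report at all.

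Second, the AESI list is narrower than the outcome it should supply. A non-severe fall in blood pressure during the infusion is part of the stated safety outcome but has no AESI line.

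**Working it through.** The documents give no figure of their own on this point, so the check is a count, a term-by-term match and one threshold calculation.

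**1. Lines limited in one arm.** The AESI list has 16 mild/moderate + 3 major = 19 lines. Limited in the infusion group: severe hypertension, severe hypotension and neurological changes (3), plus anaphylaxis-like reaction, seizures and non-reassuring fetal tracing (3), so 6 of 19. The other 19 - 6 = 13 lines have no arm-specific limit.

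**2. Is the timeframe fixed elsewhere?** The candidates are the 1-2 hour iron dextran infusion, the 20-30 minute observation after the test dose, fetal monitoring to at least 30 minutes after the infusion, the 48-72 hour call and, with ferumoxytol, two infusions 3 to 8 days apart. None is tied to the term.

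**3. The same non-serious headache in each arm.**

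| | IV arm | Oral arm |
|---|---|---|
| AESI line | neurological changes | neurological changes |
| Time limit | infusion timeframe, undefined | none stated |
| First reported at | 48-72 hour call | 2-4 week contact |
| Must be logged? | not if outside the timeframe | yes |

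**4. When could this matter in a comparison?** Suppose a line were compared by two-sided Fisher test with no IV event counted. With k oral events and n per arm, p = 2 × C(n,k) / C(2n,k). The plan gives n = 108/2 = 54 evaluable or 120/2 = 60 recruited.

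| IV vs oral events | p, n = 54 | p, n = 60 |
|---|---|---|
| 0 vs 5 | 0.0567 | 0.0573 |
| 0 vs 6 | 0.0270 | 0.0274 |
| 1 vs 7 | 0.0602 | 0.0612 |
| 1 vs 8 | 0.0314 | 0.0322 |

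A line with fewer than six oral events cannot reach p ≤ 0.05 in this direction, so rare events such as seizures are barely touched. The line that combines headache, dizziness and syncope is the likeliest to be affected.

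**5. Illustration on assumed rates.** Assume equal true weekly rates r in both arms, a 3 hour IV window and n = 54. Then the IV probability is 1 - (1 - r)^(3/168), and the oral probability is capture × [1 - (1 - r)^weeks]. The chance of p ≤ 0.05 from the windows alone is:

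| Oral counting | r = 0.5% | r = 1% | r = 2% |
|---|---|---|---|
| 10 weeks, all captured | 4.7% | 41% | 94% |
| 10 weeks, half captured | 0.2% | 4.3% | 37% |
| 10 weeks, a quarter captured | 0.01% | 0.2% | 3.6% |
| 4 weeks, all captured | 0.1% | 1.9% | 24% |

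An added one-off infusion risk of 2% in the IV arm lowers the first row to 1.8%, 20% and 75%. Rates, capture, weeks and added risk are all assumptions. The results run from almost nothing to almost certainty, so the documents do not fix the size.

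**6. Outcome terms against the AESI list.** Counted by commas, the safety outcome has 17 + 3 = 20 terms, with hypertension or hypotension as one.

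| Outcome term | In the AESI list | Strength of the gap |
|---|---|---|
| hypertension or hypotension | severe only; abnormal vital signs excluded as such | clear |
| numbness | not named | holds unless the bracket after neurological changes is only illustrative |
| back or joint aches | new onset only | weak: arthralgia is listed without limit |

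Read strictly, that is 3 of 20. Other conventions give 2 of 20 (new onset not treated as a limit), or 3 or 4 of 21 (blood pressure split in two). The blood pressure gap remains under all of them.

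**The case against.** The strongest reply is that the outcome is infusion reactions, which women assigned to oral iron are not planned to have, so a limit to the infusion suits it. No per-line test between arms is specified, and the general rule on categorical variables applies only as appropriate. This stands in part. A reader might infer that the plan contains a biased between-arm safety test; it does not. What remains is an objective worded as a comparison, AESIs collected in both arms, and no statement that they will not be compared.

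There are also safeguards. Every SAE and AESI needs a judgement on its relationship to the drug, which would separate some background oral-arm events, and serious events are reported in both arms. Both reduce the tilt. Neither recovers a non-serious IV event that was never logged, and in an open-label trial the judgement is made with the arm known.

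A reader might also infer that the outcome data are certainly lost. The documents do not go so far. The Case Report Forms section says that eCRFs hold all subject data, the schedule of events has a post-infusion call for adverse events, and infusion monitoring data come from the EMR. The eCRF itself is not among the documents. These statements conflict with the AESI-only rule and must be reconciled.

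Finally, the AESI wording behind the second gap is the same for both arms, so it is tempting to call the outcome incomplete in both. Because the outcome is defined as infusion reactions, the loss falls on the IV arm's outcome.

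**Conclusion.** The concern holds in a bounded form. Six of 19 AESI lines, including all three major reactions, are limited in the IV arm only to a period that is not defined. Non-serious IV events on those lines outside that period need not be logged. If oral-arm events are counted over a longer period, as contacts running to delivery suggest but no passage states, a comparison of these lines would favor IV iron. The size cannot be derived, and the high percentages in the illustration should not be read as an estimate of it. A rate of reactions during the infusion in the IV arm alone is unaffected by the unequal windows, though it does need the timeframe defined.

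Separately, the infusion-reaction outcome is not fully matched by its capture list. The blood pressure gap is clear, numbness is probable and aches are weak.

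The primary outcome, the sample size and SAE reporting are untouched. Confidence is high for the counts and conditional for the tilt. Severity is minor to should-fix.

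**What to change.** - **Reconcile the safety outcome, the AESI-only rule and the AESI list.** Record every safety outcome term with its severity: name numbness, record hypertension and hypotension of any grade and exempt them from the vital-signs exclusion, and align the aches wording.
- **Define the start and end** of the infusion timeframe, including how it applies when there are two infusions.
- **Log AESIs in both arms without an arm-specific limit**, and add onset date to the event report. The timeframe then becomes an analysis category and no longer decides what is recorded.
- **State the analysis.** Report infusion-timeframe reactions descriptively for the IV arm, and compare arms only over a common window, such as randomization to delivery.

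An optional addition is the oral arm's side-effect checklist for the IV arm at 2-4 weeks and at delivery. Without it, a common window still rests on unequal contacts, and the report should say so. As a clarification only, the sections on risk protection and event assessment should say, as the treatment section does, that with ferumoxytol the call follows the second infusion.

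The cost is protocol and CRF wording, one date field, and more non-serious AESIs logged in the IV arm. The optional checklist adds one or two short contacts for about 60 women. No treatment changes.
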